10.2.9 Projected Timetable

Study enrollment will occur over a 12-month period. The study intervention and follow-up phase will go on for a total of 16 months.

10.3 Validity and Reliability of Outcome Measures

See above.

11.0 STUDY TREATMENTS

11.1 Study Interventions

All participants will receive medication management and contingency management interventions.

11.1.1 Active Group

Participants randomized to NAC will receive double-blind NAC 1200 mg to be taken twice daily throughout the 12-week active treatment. Individuals experiencing intolerable adverse effects may undergo a dose reduction to 600 mg twice daily or the medication may be discontinued altogether, based on the judgment of the study medical clinician.

11.1.2 Control Group

Participants randomized to placebo (PBO) will receive double-blind PBO to be taken twice daily throughout the 12-week active treatment. As with those in the active treatment group, individuals experiencing intolerable adverse effects may undergo a dose reduction to 600 mg twice daily or the medication may be discontinued altogether, based on the judgment of the study medical clinician.

11.1.3 Dispensing of Study Medications

United States Pharmacopeia (USP) grade NAC powder will be encapsulated in 600 mg quantities (two 600 mg capsules per dose). Matched placebo capsules will also be prepared. Riboflavin 25 mg will be added to all capsules as a biomarker for medication compliance. All capsules will be packaged in blister packs, with individual labels for time/date of each dose (e.g., Tuesday morning October 5th). This date- and time-labeled blister pack method has demonstrated superior participant adherence, compared to traditional packaging, and offers the additional advantage of tracking the timing of any missed doses (Wright et al., 1999; Huang et al., 2000; Simmons et al., 2000). We successfully used identical methods for medication/placebo preparation and dispensing in our adolescent study.

11.1.4 Provisions for Access to Investigational Treatment After Study

NAC is readily available over-the-counter and may be accessed by participants after the study if desired.

11.2 Drug Packaging/Handling/Storage/Accountability

NAC and matched placebo will be packaged and distributed by the appropriate agency contracted by NIDA. It will be stored at each site in compliance with all state and institutional policies. While at each site, study drug will be refrigerated, and temperatures should be between 36 and 46 degrees Fahrenheit (2 – 8 degrees Celsius). A temperature log will be maintained to ensure study drug is maintained at the correct temperature. Drug-accountability records will be maintained at all times. These will include a record of the quantity of medications transferred between areas of the study site (from pharmacy to clinic and back, for example), and those dispensed to and returned by an individual participant.

11.3 Training Procedures

Medication Management

Given that medical clinicians already provide medication management as part of routine clinical care, significant training for the medical clinicians will not be necessary. Medical clinicians will be trained in medication management during the national training.

Contingency Management

Research staff will be trained in contingency management during the national training. Training will include basic principles of contingency management as well as training on the use of the incentive calculator (to be developed by the Lead Team).

Fidelity of Contingency Management

Contingency management for both attendance and abstinence will be tracked on a running log for each participant. The Contingency Management Tracker will capture visit date, compliance (yes/no), presence of cannabinoids in the urine (yes/no), incentive earned based on the incentive calculator, as well as actual incentive provided to the participant. This information will be reviewed by the local QA monitor at each monitoring visit for accuracy.

12.0 CONCOMITANT THERAPY

12.1 General Considerations

Concomitant medications that either pose a safety risk or may confound the primary efficacy measure will not be allowed.

The local site medical clinician should examine the acceptability of all concomitant medications not explicitly prohibited. In order to ensure that appropriate concomitant therapy is administered, it is essential that study participants be instructed not to take any medication (either self-administered non-prescription products or prescription medication prescribed by another physician) without prior consultation with the research staff.

The generic name, start date, end date, dosing information and indication for any medication (prescription or non-prescription) will be recorded on the prior/concomitant medication form.

Each participant will be instructed not to consent to any elective medical procedure without prior consultation with the research staff. An elective procedure (minor surgery, dental surgery, orthopedic surgery, etc.) that might require hospitalization or anesthesia should be deferred until after the study whenever clinically appropriate.

12.2 Medications Prohibited Before/During the Trial

Due to potential interactions with NAC, participants may not take nitroglycerin or carbamazepine 14 days before randomization or any time during participation in the study. Individuals receiving maintenance buprenorphine or methadone treatment will be excluded from the study. Participants will be asked not to use synthetic cannabinoids (e.g., K2/Spice) or take cannabinoid medication (e.g., dronabinol/oral tetrahydrocannabinol) during the course of the study, as these substances may confound outcomes. Participants will be asked not to start taking multivitamins containing riboflavin during study participation to avoid interference with medication compliance tracking. However, participants should continue to take any multivitamins they were on at the screening/baseline assessment.

Additionally, participants will be advised not to take non-study NAC or NAC-containing products throughout study participation.

12.3 Medications Allowed During the Trial

Aside from the above-mentioned exclusionary medications, participants may take other medications as deemed appropriate by the study medical clinician.

13.0 STATISTICAL ANALYSIS

13.1 General Design

CTN-0053 is a two-armed, multisite, randomized controlled trial comparing NAC to PBO, built upon a platform of CM, in terms of abstinence over the 12 weeks of treatment. The target sample size is 300. The Statistical Analysis Plan will contain detailed information regarding randomization, power, and sample size calculations, planned analyses and content for reporting results.

13.1.1 Study Hypothesis

It is hypothesized that cannabis abstinence rates in the NAC-treated participants will be greater than in the participants randomized to receive PBO.

13.1.2 Primary and Secondary Outcomes (Endpoints)

The primary outcome of CTN-0053 is the abstinence rate over the 12 weeks of treatment. Abstinence is based on a weekly urine drug screen (UDS) analyzed by central laboratory testing and defined as a negative cannabinoid result. The first UDS contributing to the primary outcome will be collected at Week 2, since the Week 1a Visit UDS sample is collected prior to randomization. The last UDS contributing to the primary outcome will be collected at the End of Treatment (Week 13) Visit. Thus, each participant contributes 12 indicators of abstinence, one for each week of treatment, and the primary outcome measure for each participant is then a vector of binary variables of length 12. The primary end result will indicate whether the likelihood of a negative urine cannabinoid test in NAC participants is statistically different than in PBO participants over the entire 12 weeks of treatment.

The CTN TEAM Task Force recommends testing for a treatment effect only in the last four weeks of the active treatment phase. This study will instead consider the entire treatment period because we are seeking to replicate, within a preliminary Phase III design, findings from the adolescent study, which also considered the entire treatment period. We nonetheless assessed the feasibility of using the CTN TEAM Task Force recommendation within this study and found that, with the proposed sample of 300 participants, we are reasonably powered (see Section 13.2) for a four-week end-of-treatment abstinence outcome. This will be used as the main secondary outcome, and we will additionally explore two-week end-of-treatment abstinence.

One objective of the proposed study is to replicate the findings from the adolescent study previously conducted by the LN. For this reason, additional analyses will be performed that mimic those conducted for the adolescent study. The first analysis will be the comparison of the odds of a weekly cannabinoid-negative urine drug screen during the first 8 weeks of treatment across treatment assignments. In addition, a modified end-of-treatment analysis will be used that is based on the first 8 weeks of treatment such that one outcome variable is defined by UDS-based abstinence in weeks 6-9 (corresponding to four-week "end-of-treatment") and another will be defined as UDS-based abstinence in weeks 8-9 (corresponding to two-week "end-of-treatment"). Conducting these analyses will allow direct comparison of results with the adolescent study which utilized only 8 weeks of active treatment.

All of the end-of-treatment analyses will be repeated using a different definition of abstinence that requires both negative urine drug screens as well as self-reported abstinence on TLFB. An additional secondary abstinence outcome will be to use the methodology developed by Huestis and colleagues to utilize urine cannabinoid and creatinine testing to distinguish cannabis

abstinence versus new use (Schwilke et al., 2011). This methodology uses the actual quantitative results of the UDS, whereas the primary outcome measure assesses abstinence using the qualitative UDS results from the central laboratory. Another secondary outcome will be abstinence defined solely through self-report, which is collected via Timeline Follow-Back. Potential secondary outcomes other studies have used: longest period of continuous abstinence, and number of negative urines.

Additional secondary outcomes include: (i) other cannabis-related measures of craving, withdrawal, and compulsive use; (ii) cannabis-related problems; (iii) other substance use; and (iv) overall quality of life.

13.1.3 Factors for Stratification

Participants will be randomized to one of two arms, NAC or PBO, in a 1:1 fashion. Randomization will be stratified by site and self-reported tobacco smoking status. Prior research indicates that cannabis users who also smoke tobacco may have more difficulty with cannabis cessation than those who do not smoke tobacco (Peters et al., 2012).

13.1.4 Statistical Methods for Primary and Secondary Outcomes

Please note that the Randomization Visit where participants first receive study drug is Week 1a. Thus, 12 weeks of active treatment will go through week 13 (End of Treatment).

For the primary outcome measure, a longitudinal logistic model will be used to analyze the odds of a negative UDS as an indicator of abstinence across all 12 weeks of treatment (measured at weeks 2-13 [End of Treatment]). At each week, the primary outcome will be an indicator of whether the urine drug screen at that visit was negative for cannabinoids. Since each participant will contribute up to 12 outcomes to the model, generalized estimating equations (GEEs; Liang and Zeger, 1986) will be used to adjust for this correlation. The primary analysis will assess various correlation structures between observations and select the best fitting structure using the QIC criterion. The longitudinal model will include the main effect of treatment, the main effect of time, site effects, the effect of being a tobacco smoker at baseline and a time-by-treatment interaction. These terms may be dropped from the final model depending on evidence of an effect; however, the following terms are always included: treatment assignment, baseline tobacco smoking status, and site. Testing of the treatment difference will evaluate whether the coefficient of the main effect of treatment assignment is significantly different from zero.

Let y_{it} denote the indicator of abstinence for participant i (i=1, ..., 300) and t indexes week (t=2, ..., 13), that is $y_{it} = 1$ for a cannabinoid negative urine drug screen and 0 for a positive result. Missing UDS will be coded as missing (and counted as positive/non-abstinent) for the primary analysis, but sensitivity analyses will be performed, as described in **Section**

13.3. The longitudinal model is given by:

logit P(
$$y_{it} = 1$$
) = $\alpha + \eta^*I\{Smoker\} + \beta I\{NAC\} + \phi_t \times I\{t\} + \gamma_t \times I\{NAC\} \times I\{t\} + \Sigma_{sites} \theta_{sites} \times I\{site\}$

where I{} is an indicator function defined in a qualitative manner using (k-1) indicator variables to capture k categories, where k=2 (two treatments) for I{NAC}, k=12 (12 weeks) for I{t} and k=X (X sites) for I{site}. For example, if there are four sites then I{site} would be defined using three indicator variables. Entering time in the model this way allows for a different abstinence rate at each week. The odds ratio (OR) capturing the main effect of treatment is e^{β} , thus the null hypothesis is $\beta = 0$, and the alternative is $\beta \neq 0$. Should there be evidence of a time-bytreatment interaction, secondary tests of treatment effect will also evaluate whether $y_t = 0$.

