In addition to providing contingent reward for cannabis abstinence (negative urine cannabinoid dipstick tests), we propose providing contingent reward for visit attendance (i.e., keeping scheduled study visits). This "two-tiered" CM approach was used with significant effect on both study retention and cannabis abstinence in a prior young adult CM trial (Carroll et al., 2006). An additional potential benefit of the "two-tiered" approach is that it increases early exposure to contingent rewards. Among regular cannabis users, urine cannabinoids may take two to four weeks to test negative after initiation of abstinence. In the context of a CM procedure that only rewards negative urine testing, several participants, even if abstaining from use, would potentially not be eligible for rewards for two to four weeks after achieving abstinence. It is felt that rewarding attendance may help to sustain motivation among participants initiating a quit attempt. We are particularly interested in this two-tiered method of reinforcement given the lack of single-tiered CM (reward only for substance abstinence) effect on study retention in our prior adolescent smoking cessation study (Gray et al., 2011).

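### The primary test of beta = 0 addresses one unnamed reference week if the week-by-treatment interaction is kept and the 12-week effect only if it is dropped, and no rule says which

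*Protocol*

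**What the plan says.** In Section 13.1.2 the primary question is put in these terms: "likelihood of a negative urine cannabinoid test in NAC participants is statistically different than in PBO participants over the entire 12 weeks of treatment".

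Section 13.1.4 turns this into a longitudinal logistic model fitted by GEE. The model contains treatment, week, site, "the effect of being a tobacco smoker at baseline and a time-by-treatment interaction". Each categorical term is "defined in a qualitative manner using (k-1) indicator variables to capture k categories", with k = 12 for week. The section adds: "Entering time in the model this way allows for a different abstinence rate at each week". It names e^β as the odds ratio for the main effect of treatment and sets β = 0 as the null: "Testing of the treatment difference will evaluate whether the coefficient of the main effect of treatment assignment is significantly different from zero".

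Two further sentences matter. On model reduction: "These terms may be dropped from the final model depending on evidence of an effect"; only treatment, baseline smoking and site are protected. On interaction: if there is evidence of one, "secondary tests of treatment effect will also evaluate whether" the week-specific interaction coefficients are zero.

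Section 13.2, step 8, says the power simulation also used a model with the week-by-treatment interaction. It reports power of .84 (OR = 2) and .93 (OR = 2.25) for 300 participants at 6 sites.

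**The concern.** With (k-1) indicators for week and their products with treatment, the log odds ratio for NAC is β in the omitted week and β + γ_t in any other week t. So β = 0 is a statement about one week, and the section does not say which. Calling e^β the main effect does not make it an average.

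The permission to drop terms does not settle the matter. It gives the test two possible meanings and lets the outcome data choose between them, with no stated criterion. The one-week meaning applies exactly when the data suggest that the effect varies over time, which is when a single week represents the 12 weeks least well.

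The tests of γ_t do not repair this. γ_t = 0 asks whether week t differs from the reference week, not whether NAC works in week t.

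At stake is which hypothesis the trial's primary p-value belongs to, and whether the power table describes that test.

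**Working it through.** **1. Meaning of β.** With t = r as the omitted week, logit P(NAC, t) − logit P(PBO, t) = β + γ_t, where γ_r = 0.
- Interaction kept: β is the log OR in week r only.
- Interaction dropped: β is a common log OR over weeks 2–13.
- 12-week average: β + (1/12)Σγ_t.

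**2. Inputs (Section 13.2).** There are 300 participants, taken as 150 per arm under 1:1 allocation. Placebo rates for weeks 2–9 are .20, .33, .40, .41, .40, .37, .36, .50, and weeks 10–13 repeat weeks 6–9. The OR is 2 or 2.25 in every week, AR(1) correlation is 0.75, 57% are smokers, and missing tests count as positive. Summing the 105 missing-data patterns gives 74, 72, 69, 70, 65, 62, 64 and 64 tests observed in weeks 2–9. I took weeks 10–13 to have the observed shares of weeks 6–9.

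**3. The plan's own figure.** I simulated steps 1–8 with first-order Markov binary data and an AR(1) GEE with robust SE. The 12-week average contrast, with the interaction in the model, has power 0.82–0.84 at OR = 2 (stated .84) and 0.91–0.93 at OR = 2.25 (stated .93). The stated figures therefore fit a 12-week average effect.

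**4. One-week test, closed form.** With f the observed share, the rates after missing = positive are a = f·p₀ and b = f·p₁, where p₁ has odds OR × p₀/(1−p₀). Power = Φ{[(b−a) − 1.96·SE₀]/SE₁}, with SE₀ pooled and SE₁ unpooled.
- Week 2: p₀ = .20, p₁ = .333, f = 74/105 = .705, so a = .141 and b = .235. SE₀ = .0451, SE₁ = .0448. Power = Φ[(.0940 − .0884)/.0448] = Φ(0.12) = 0.55.
- Week 13: p₀ = .50, p₁ = .667, f = 64/105 = .610, so a = .305 and b = .406. SE₀ = .0553, SE₁ = .0550. Power = Φ[(.1016 − .1083)/.0550] = Φ(−0.12) = 0.45.
- All weeks: from 0.45 (weeks 9 and 13) to 0.59 (week 3).

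**5. Candidate tests compared**

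| Test | OR = 2 | OR = 2.25 |
|---|---|---|
| β, interaction kept, reference week 2 (simulated) | 0.54–0.57 | 0.69–0.70 |
| β, interaction kept, reference week 13 (simulated) | about 0.46 | 0.55–0.56 |
| β, interaction dropped | about 0.81 | about 0.91 |
| Kept only if joint interaction p < 0.05 (assumed rule), reference week 2 | about 0.79 | about 0.89 |
| 12-week average, interaction kept | 0.82–0.84 | 0.91–0.93 |

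Under the assumed p < 0.05 rule the interaction stayed in about 8–10% of simulated trials.

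**6. If effects do vary.** Section 9.5.1 notes that "urine cannabinoids may take two to four weeks to test negative after initiation of abstinence", so a delayed effect is conceivable. As an illustration only, take ORs of 1.0, 1.27, 1.61 and 2.05 in weeks 2–5 and 2.6 thereafter. The average contrast then has power 0.85. β has 0.04 with week 2 as reference but about 0.68 with week 13 (closed form). Test-then-drop with reference week 2 has 0.57. The result turns on a coding choice that the protocol does not make.

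**The case against.** The strongest reply is that the intent is plain. Section 13.1.2, the opening of 13.1.4 and step 8 all speak of the whole treatment period, and the sample size reproduces for a 12-week effect. The interaction is not a protected term. Under the constant OR used for planning it would usually be dropped, leaving about 80% power, and the adolescent trial saw no treatment-by-time interaction (p = 0.75, Section 4.2.2). Section 13.1 leaves analysis detail to the SAP.

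Much of this stands. A reader might infer that the trial has about 56% power instead of 84%. The documents do not support that: the figure needs the interaction to be kept and week 2 to be the reference, and the protocol fixes neither. Nor is .84 a wrong figure for a 12-week effect. The delayed-effect scenario has no source in the documents. No material inflation of false positives from the selection step was shown: simulated null rejection for test-then-drop was 0.057 in one run, and in another 0.062 against 0.061 for the no-interaction model.

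What does not stand is the appeal to intent or to the SAP. Section 13.1.4 already states the model, the coding, the null hypothesis and the permission to drop terms. Together they define a test that does not match the stated question whenever the interaction is retained.

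**Conclusion.** The primary test is wrong as written. With the interaction kept, β = 0 concerns one unnamed week, with power of about 45% to 59% at OR = 2 depending on the week. With it dropped, β is a common 12-week effect, with power of about 80%. An unspecified, data-driven step chooses between them. The stated .84 and .93 are consistent with a 12-week average effect and not with the reference-week coefficient. The trial is not shown to be underpowered for the effect it intends to test.

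The structural point follows from the text alone. The power figures rest on assumptions: the site effects for the primary outcome are in a figure not shown, so the six values given for end-of-treatment abstinence were used, and smoking was given no effect. Average-effect power at OR = 2 ranged from 0.76 to 0.91 across ways of generating correlated binary data, so the close match to .84 depends partly on the generator. The one-week figures were stable (0.54–0.57 for week 2, 0.43–0.48 for week 13).

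**What to change.** - Prespecify one primary test, whatever the interaction result: the average week-specific log odds ratio over weeks 2–13, β + (1/12)Σγ_t with γ = 0 for the reference week, using the robust SE. This equals β under sum-to-zero coding of week.
- Do not offer a model without the interaction as equivalent. When effects differ by week it estimates a weighted log odds ratio, not the equal-weight average.
- Always keep week in the model, along with treatment, smoking and site. Remove only the permission to drop terms; the rest of that sentence protects the other three and should stay.
- Report week-specific effects as tests of β + γ_t = 0, and describe tests of γ_t = 0 as tests of interaction.
- State in Section 13.2 that the power figures refer to the 12-week average contrast, after confirming this in the original simulation code.

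The cost is protocol and SAP wording only, with no new data or participants. It should be done before unblinding.

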13.2 Sample Size and Statistical Power

As per CCTN's recommendation for CTN-0053 to closely mimic the adolescent study, we conducted the sample size calculation using the approach described below. Please note that the adolescent study numbering for weeks began with randomization at week 0, and subsequent weekly observations during treatment at weeks 1-8 (8-week trial). However, in contrast, the current study begins with randomization at week 1, and subsequent weekly observations during treatment at weeks 2-13 (12-week trial). As such, for example, week 1 in the adolescent study corresponds to week 2 in the current study.

Sample Size Calculation Approach:

[figure not shown]
1. Obtain the proportions of negative UDS in each week in the Placebo + CM arm from the adolescent study. Only 52/105 participants with positive baseline UDS in the Placebo + CM were used and missing UDS were not imputed while calculating these proportions.

Week	1	2	3	4	5	6	7	8
Proportion	.20	.33	.40	.41	.40	.37	.36	.50

2. The following missing data patterns were observed in the 105 participants from the adolescent study. Here 0 represents missing UDS and 1 represents UDS present. For example, 00000000 denotes that all 8 UDS are missing.

UDS	Pattern	Frequency	Percent
All Missing	00000000	26	25%
	10000000	4	11%
	11000000	2	
(I)	11100000	1	
tone	11111000	2	
anol Ssir	11111100	1	
Monotone Missing	11111110	2	
	00100000	1	20% of participants had
 	01011111	1	23% of UDS missing intermittently
Intermittent Missing	01100000	1	
Mis	01110100	1	
ŧ	01110111	1	
itte	10111111	2	
Ē	11011111	3	
ıteı	11110111	3	
 	11111011	6	
	11111101	2	
All Observed	11111111	46	44%
Total		===	
		105	

- **3.** Assume two different odds ratios (OR = 2.25 and 2) as effect size measures. We assumed auto-regressive (AR(1)) correlations of 0.75 for the within-participant correlation in weekly scores over time, and a baseline tobacco smoking rate of 57% obtained from the adolescent study.
- **4.** Impose fixed site effect (6 sites) that would change the proportion of negative UDS in each of the sites. This will induce the site variability. Below are the proportions of negative UDS in the two arms with treatment effect, OR = 2.25. Similar plots can be obtained for OR = 2, as well as 4 and 5 sites.

- **5.** Simulate the data assuming the proportions from Step 4 and that abstinence rates in weeks 10-13 are the same as weeks 6-9.

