13.4 Significance Testing

The primary outcome will be evaluated using a two-sided test with a type I error rate of 5%. There are several secondary outcomes; however, multiple comparisons will not be adjusted for since these are not part of the study's primary objective.

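### If the NAC effect varies by week, Section 13.1.4 tests change from an unnamed reference week and calls it a test of treatment effect

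*Protocol*

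**What the plan says.** Protocol Section 13.1.4 gives a longitudinal logistic model fitted by GEE. Its terms are an intercept, baseline smoking, treatment (β), week (φₜ), treatment by week (γₜ) and site. The indicators are "defined in a qualitative manner using (k-1) indicator variables to capture k categories", so 12 weeks give 11 week indicators and 11 interaction coefficients. No reference week is named. On the purpose of the week terms the section says: "Entering time in the model this way allows for a different abstinence rate at each week".

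The primary test is on β: "Testing of the treatment difference will evaluate whether the coefficient of the main effect of treatment assignment is significantly different from zero". Of the model terms, "These terms may be dropped from the final model depending on evidence of an effect"; only treatment, smoking and site are always kept.

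If an interaction is found, "secondary tests of treatment effect will also evaluate whether" the interaction coefficient is zero. The extracted text prints this symbol as y with subscript t. Since y denotes the outcome in the same section, γₜ is the only sensible reading.

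Section 13.4 adds: "The primary outcome will be evaluated using a two-sided test with a type I error rate of 5" per cent. It makes no multiplicity adjustment for secondary outcomes.

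**The concern.** The sentence applies only once the NAC effect is thought to differ between weeks. The question then is in which weeks NAC works. A test of γₜ = 0 answers a different question: in which weeks the effect differs from that in one particular week. The reference week itself has no γ at all.

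What is at stake is how a time-varying result would be reported. A week in which NAC does nothing can be listed as showing a significant treatment effect, because the reference week had one. A week with a real effect can be listed as null, because it matches the reference week.

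The situation is plausible. Section 9.5.1 notes that urine can take two to four weeks to turn negative after a regular user stops, so an effect on urine tests could appear late. The adolescent trial found no treatment-by-time interaction (p = 0.75, Section 4.2.2), but it treated for 8 weeks and this trial treats for 12.

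**Working it through.** **Algebra from the printed model.** With smoking and site held fixed:

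- log odds ratio for NAC in week t = β + γₜ
- in the reference week γ is absent, so β = log(OR_ref)
- hence γₜ = log(ORₜ) − log(OR_ref) = log(ORₜ / OR_ref)

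γₜ = 0 therefore means ORₜ = OR_ref. It means no treatment effect only if OR_ref = 1. Under sum-to-zero coding γₜ would be a deviation from the average effect, which is still not a treatment effect.

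**Worked case.** Let the odds ratio be 2.25 in weeks 2–7 and 1.0 in weeks 8–13, with week 2 as reference, so β = ln 2.25 = 0.81.

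| Week | True OR | γₜ | β + γₜ |
|---|---|---|---|
| 5 | 2.25 | 0 | 0.81 |
| 8 | 1.0 | −0.81 | 0 |

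The γ column is zero where NAC works and non-zero where it does not. Read as a treatment effect, exp(γ₈) = 1/2.25 = 0.44 would even look like harm.

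**Simulation inputs from the protocol.** N = 300, 1:1 (Sections 9.4 and 13.1). Placebo weekly rates .20 .33 .40 .41 .40 .37 .36 .50 for weeks 2–9 (Section 13.2: "Obtain the proportions of negative UDS in each week in the Placebo + CM arm from the adolescent study"), with weeks 10–13 equal to weeks 6–9. The adolescent missing-test patterns, with missing set to positive. Effect sizes from "Assume two different odds ratios (OR = 2.25 and 2) as effect size measures" guide the step scenarios.

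**Assumptions not in the protocol.** Latent AR(1) correlation (.85 for the scenarios below); extension of the missing patterns to 12 weeks; choice of reference week; and an 11-df joint Wald test at 5% as the evidence of interaction. The scenario odds ratios apply before missing tests are set to positive. After that step a constant 2.25 becomes about 1.82.

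**Reproducing the plan's power first.** For 6 sites and N = 300 the protocol states .93 (OR 2.25) and .84 (OR 2) over 12 weeks. The common-effect GEE test gives .927 and .846 at latent correlation .80, and .907 and .824 at .85. The 8-week figures (.88, .78) are matched at .87 (.882, .764). No single latent value matches both tables, but the set-up is close to the protocol's.

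**Linear fade, OR 2.5 in week 2 to 1.0 in week 13, reference week 2.** The interaction test is significant in about 35% of trials. In those trials γ₁₃ = 0 is rejected about 90% of the time, so 0.35 × 0.90 ≈ 0.31 of all trials. β + γ₁₃ = 0 is rejected about 7% of the time in the same trials.

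**Step patterns, rejection rates given a significant interaction test** (it is significant in 72% of trials for the fade and 62% for the delay):

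| Pattern and reference week | Weeks with no effect: γₜ = 0 | Weeks with no effect: β + γₜ = 0 | Weeks with OR 2.25: γₜ = 0 | Weeks with OR 2.25: β + γₜ = 0 |
|---|---|---|---|---|
| Fade (2.25 weeks 2–7, then 1.0), week 2 | 59–68% | 5% | 7–9% (weeks 3–7) | 68–76% |
| Same fade, week 13 | 6–7% | 5% | 64–67% | 67–77% |
| Delay (1.0 weeks 2–5, then 2.25), week 13 | 37–53% | 5% | 7–10% (weeks 6–12) | 59–70% |
| Same delay, week 2 | 7% | 5% | 37–51% | 59–70% |

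Repeat runs agree to within a few points. In the first and third rows the stated test reverses the picture. In the second and fourth the reference-week effect is zero, so γₜ equals the weekly effect and the loss is essentially one of power.

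**The case against.** The tests are secondary and conditional. Without that condition γ₁₃ = 0 is rejected in about 65% of trials under the linear fade, and a reader might take that as the error rate. It is not: the protocol runs these tests only after evidence of interaction, and the rate over all trials is about 31%. This stands.

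A reader might also infer that a steady NAC effect would be missed. The protocol does not support that. With a constant odds ratio of 2 the interaction test is significant in only about 8% of trials, so the γₜ tests seldom run and the common-effect test applies.

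Nor will errors always occur in both directions. As the table shows, the outcome depends on the reference week.

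Time-specific effects are examined elsewhere too: the weeks 2–9 analysis, abstinence anchored at the end of the eighth treatment week, and two- and four-week end-of-treatment abstinence (Sections 8.2 and 13.1.2). The γₜ tests are an addition to these. That limits the consequence but does not correct the hypothesis.

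It can be said that the SAP will supply the detail, as Section 13.1 promises. But this is not an omission. The protocol states a specific hypothesis, and an SAP would be expected to carry it forward.

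Finally, the sentence might be read as the interaction test itself. That would be circular, since it applies only once an interaction has been found, and the text calls these tests of treatment effect.

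**Conclusion.** The sentence is wrong as written. The algebra follows from the printed model and its coding, and nothing elsewhere in the protocol corrects it. Once triggered, the error can be large: with a step fade and reference week 2, rejection is 59–68% in weeks with no effect and 7–9% in the other weeks with odds ratio 2.25, against 5% and 68–76% for the proper contrast. With a reference week in which NAC has no effect, only power is lost.

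These sizes rest on the assumed latent correlation, reference week, effect patterns and interaction criterion; the algebra rests on none of them.

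A reader might infer that this sentence undermines the primary result. It does not: the primary test, its 5% level and the sample size are untouched by it. Reading β as an overall effect while the interaction stays in the model is a related but separate issue.

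**What to change.** Replace the sentence with wording such as:

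> If the joint 11-df test of all γₜ indicates a treatment-by-week interaction, the NAC effect in each week will be estimated as exp(β + γₜ) with a 95% confidence interval and tested by the contrast β + γₜ = 0, as secondary analyses unadjusted for multiplicity.

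Reserve γₜ = 0 for the interaction test and name the reference week. In the reference week the contrast reduces to β. The multiplicity clause matters because this gives twelve weekly tests at 5%; it is consistent with Section 13.4.

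The cost is one sentence in the protocol, carried into the SAP. The contrasts come from the same fitted model, with no new data and no change in sample size.
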